**Table CGM-1: Summary of main comparisons for the CGM ancillary study**

Aim	Outcomes	Contrast	Timing
Primary - 10.4	Mean glucose, TIR, CV	DASH4D vs Comparison	FP week 3-5
Secondary - 10.5.1	SD, TA180, TA250, TB70, TB54	DASH4D vs Comparison	FP week 3-5
Secondary - 10.5.2	See 10.3 for full list	DASH4D vs Comparison	FP week 3-5
Sensitivity analysis 1a	Mean glucose, TIR, CV	DH vs DL; CH vs CL	FP week 3-5
Sensitivity analyses 1b	Mean glucose, TIR, CV	(DH-DL) vs (CH-CL)*	FP week 3-5
Sensitivity analysis 2	Mean glucose, TIR, CV	DASH4D vs Comparison (Per-protocol)	FP week 3-5
Sensitivity analysis 3	Mean glucose, TIR, CV	DASH4D vs Comparison (CGM wear time >70%)	FP week 3-5

Note: All analyses will be conducted using an intention-to-treat approach unless otherwise stated.
 
Abbreviations: TIR = time-in-range; CV = coefficient of variation; SD = standard deviation; TA180 = time above 180 mg/dL; TA250 = time above 250 mg/dL; TB70 = time below 70 mg/dL; TB54 = time below 54 mg/dL; CH = Comparison diet with higher sodium; CL = Comparison diet with lower sodium; DH = DASH4D diet with higher sodium; DL = DASH4D diet with lower sodium; FP = feeding period
 
*Examination of interaction (difference of differences)
			

# Appendix C: Statistical Analysis Plan

## DASH4D Statistical Analysis Plan Version 1.1 July 26, 2024

### HISTORY OF STATISTICAL ANALYSIS PLAN CHANGES

The following table summarizes substantive changes between Statistical Analysis Plan (SAP) versions. Minor changes, such as minor corrections and clarifications, page numbering, and formatting are not described in the table but can be seen in the track changes version of the document.

SAP version	Affected section(s)	Brief description of change	Brief rationale for change
v1.0 (10-27-2024)	Initial complete version of the DASH4D Statistical Analysis Plan.		
v1.1 (07-26-2024)	1 Introduction; 2.1.1 Primary outcome; 2.1.2 Secondary outcome; 4.2 Primary outcome and primary testing contrast	Clarified that the primary and secondary outcome blood pressures are the average of the daily averages, rather than the average of all available measurements.	SAP was not previously clear, and the DSMB recommended that we clarify how the averages would be calculated in the event of missing data points.
	1.2.8; 4.7 Subgroup analysis	Added baseline number of medications used to treat the outcome as a pre-specified subgroup analysis.	Number of medications may be an important factor in examining the effects of the study diets on the outcomes. At the time of addition of this subgroup analysis, no analyses related to baseline medication use have been performed.
	4.1.1 Analytic population	Updated the analytic population to reflect that participants who do not have at least 1 end-of-period BP measurement will be excluded from the analysis population.	Inclusion of participants lacking any end-of-period BP data points would require changing the modelling approach, which relies on having at least 1 end-of-period BP data point.

## 1 INTRODUCTION

The objective of the DASH4D trial is to determine the effects, alone and combined, of (a) the DASH4D diet (a DASH-style diet modified for people with diabetes) vs. comparison diet that is typical of what many Americans with diabetes eat and (b) lower sodium intake vs. higher sodium intake on blood pressure (BP). The study population includes approximately 100 adults who have Type 2 diabetes, a systolic BP of 120-159 mmHg, and diastolic BP <100 mmHg (see DASH4D protocol section 6.2 for the full eligibility criteria). The core design is a single-site, four-period, crossover feeding study with 5-week feeding periods. Participants are fed each of four iso-caloric diets, presented in random order. The four diets are:

- the DASH4D diet with lower sodium
- the DASH4D diet with higher sodium
- the comparison diet with lower sodium
- the comparison diet with higher sodium (reference diet).

Outcomes (unless otherwise specified) are measured at the end of each feeding period, with end-of-period assessments captured during the final 2 weeks of each 5-week feeding period. In rare instances when extenuating circumstances require it, feeding and outcome assessments may be extended briefly into a 6th week to complete the end-of-period measures.

The primary outcome is end-of-period, office-based systolic BP, where seated BP is measured in triplicate on five separate days during the last 2 weeks of each 5-week feeding period, and the mean of these daily systolic BP measurements is used as the primary outcome of the corresponding feeding period.

### 1.1 Primary aim

To determine the mean difference between end-of-period systolic BP on the DASH4D diet with lower sodium and the end-of-period systolic BP on the comparison diet with higher sodium (“primary testing contrast”).

Hypothesis: Mean end-of-period systolic BP will be significantly lower on the DASH4D diet with lower sodium than mean end-of-period systolic BP on the comparison diet with higher sodium.

## 1.2 Secondary aims

- 1.2.1 To determine the mean difference between end-of-period systolic BP for the lower and higher sodium intake separately in (a) the comparison diet and (b) the DASH4D diet.
- 1.2.2 To determine the mean difference between end-of-period systolic BP for the DASH4D diet and comparison diet separately at (a) higher sodium intake and (b) lower sodium intake.
- 1.2.3 To examine whether there is an interaction between the effects of diet and sodium intake on systolic BP.
- 1.2.4 To determine the time course over 5 weeks of lower and higher sodium intakes on systolic BP in the DASH4D and comparison diets.
- 1.2.5 To determine the time course over 5 weeks of the DASH4D and comparison diets on systolic BP at lower and higher sodium intakes.
- 1.2.6 To conduct corresponding analyses (repeat above aims) with diastolic BP as the outcome.
- 1.2.7 To determine the effects, alone and combined, of the DASH4D diet (vs. comparison diet) and lower sodium intake (vs. higher sodium intake) on the other end-of-period outcomes, each from a single assessment during the final 2 weeks of each 5-week feeding period, including:
  - a. Glycemia measures, including fasting glucose (mg/dL), glycated albumin (%), fructosamine ( $\mu\text{mol/L}$ ), and HbA1c (%). Of these, our principal measures of glycemia are fructosamine and HbA1c, both of which are used clinically as integrated measures of glycemia. Fructosamine represents the average level of glycemia over 2 to 3 weeks prior to the test date, while HbA1c represents average level of blood glucose level over the preceding 3 months.
  - b. Lipid levels (mg/dL), including total cholesterol, low-density lipoproteins [LDL] cholesterol (Martin-Hopkins equation), high-density lipoproteins [HDL] cholesterol, and triglycerides
  - c. Estimated CVD risk (%): current 10-year atherosclerotic cardiovascular disease risk, using the ACC/AHA ASCVD risk equation
  - d. Orthostatic hypotension outcomes, including presence of orthostatic hypotension (yes, no), postural change in systolic BP (mmHg), and postural change in diastolic BP (mmHg)
  - e. 24-hour urinary albumin excretion (mg/24hr), which is our principal measure of urinary protein excretion; the albumin-creatinine ratio, used clinically, will also be reported
  - f. Patient-reported symptoms (any; any moderate or severe)
  - g. Diet acceptability, as rated by participants on two questions with a 9-point Likert scale for how much the participant liked the diet (1=disliked extremely, 9=liked extremely) and how hungry the participant felt while eating the diet (1=not at all hungry, 9=extremely hungry)

Additionally, safety outcomes including hypoglycemia, hypokalemia, hyperkalemia, elevated BP, low BP, serious adverse events [SAEs], and adverse medical events, which are assessed throughout each of the intervention periods, will also be documented for and compared across the study diets.

- 1.2.8 To conduct subgroup analyses (by gender, race, age, baseline level of the outcome variable [i.e., BP for the primary and secondary outcomes], baseline number of medications used to treat the outcome, and chronic kidney disease [CKD] status), corresponding to the above aims.
- 1.2.9 To establish a repository of biospecimens (plasma, serum, urine, stool, PAXgene).

## 2 OUTCOMES AND DATA SOURCES

### 2.1 Outcomes

#### 2.1.1 Primary outcome

- **End-of-period, office-based systolic BP (mmHg):** seated blood pressure will be measured in triplicate on five separate days during the last 2 weeks of each 5-week feeding period. Daily mean systolic BP (SBP) will be averaged based on the triplicate measures, and the mean of these daily SBP measurements will be used as the primary outcome of the corresponding feeding period.

#### 2.1.2 Secondary outcome

- **End-of-period diastolic BP (mmHg):** seated blood pressure will be measured in triplicate on five separate days during the last 2 weeks of each 5-week feeding period. Daily mean diastolic BP (DBP) will be averaged based on the triplicate measures, and the mean of these daily DBP measurements will be used as the secondary outcome of the corresponding feeding period.

#### 2.1.3 Other outcomes

- Other end-of-period outcomes, each from a single assessment during the final 2 weeks of each 5-week feeding period, include:
  - Glycemia measures, including fasting glucose (mg/dL), glycated albumin (%), fructosamine (μmol/L), and HbA1c (%). Of these, our principal measures of glycemia are fructosamine and HbA1c, both of which are used clinically as integrated measures of glycemia. Fructosamine represents the average level of glycemia over 2 to 3 weeks prior to the test date, while HbA1c represents average level of blood glucose level over the preceding 3 months.
  - Lipid levels (mg/dL), including total cholesterol, LDL cholesterol (Martin-Hopkins calculation), HDL cholesterol, and triglycerides
  - Estimated CVD risk (%): current 10-year atherosclerotic cardiovascular disease risk, using the ACC/AHA ASCVD risk equations
  - Orthostatic hypotension outcomes, including presence of orthostatic hypotension (yes, no), postural change in systolic BP (mmHg), and postural change in diastolic BP (mmHg)
  - 24-hour urinary albumin excretion (mg/24hr), which is our principal measure of urinary protein excretion; the albumin-creatinine ration, used clinically, will also be reported
  - Patient-reported symptoms (any; any moderate or severe)
  - Diet acceptability, as rated by participant on two questions with a 9-point Likert scale for how much the participant liked the diet (1=disliked extremely, 9=liked extremely) and how hungry the participant felt while eating the diet (1=not at all hungry, 9=extremely hungry)
- Other outcomes assessed throughout the intervention include:
  - Safety outcomes, including hypoglycemia, hypokalemia, hyperkalemia, elevated BP, low BP, SAEs, and adverse medical events

### 2.2 Data Sources

Data will include physical measurements (e.g., BP and weight), questionnaire responses (e.g., daily diaries, self-reported symptoms, diet acceptability), and laboratory tests (e.g., urinary electrolyte

excretion). Data will primarily be entered by clinic staff into a web-based data system (REDCap). Data will also be automatically transferred from central laboratories. The Data Management and Analysis Unit of the trial will oversee data storage. Backup files of the database will be generated automatically at the server level and stored at regular intervals in a secure, off-site location, to permit regeneration of the database in the event that it is destroyed. Freeze dates for data sets created for interim and publication analyses will be documented with datasets used in analyses archived in secured network attached storage (NAS) folders managed by institutional IT.

### 3 POWER AND SAMPLE SIZE

The trial aims to enroll 100 eligible participants. This sample size goal is selected based on resources and logistic considerations, after confirmation of sufficient statistical power to detect meaningful minimal detectable difference (MDD) for the primary testing contrast (see 1.1) under plausible and yet conservative parameter scenarios, as detailed below.

Minimal Detectable Difference (MDD) for systolic blood pressure (SBP) reduction between DASH4D diet with lower sodium (DL) and the comparison diet with higher sodium (CH), with 2-sided type 1 error of 0.05 and 90% power. The observed effect from the DASH-Sodium trial was 8.9 mmHg.			
Sample Size (N)	Standard Deviation (SD)	Within-person Correlation (r)	Minimal Detectable Difference (MDD), mmHg
100	14	0.5	4.71
100	14	0.75	3.34
90	14	0.5	4.99
90	14	0.75	3.53
80	14	0.5	5.28
80	14	0.75	3.84
100	12	0.5	4.04
100	12	0.75	2.86
90	12	0.5	4.28
90	12	0.75	3.03
80	12	0.5	4.53
80	12	0.75	3.21

Data from DASH-Sodium trial showed that cross-sectional SD for SBP at baseline and after intervention ranged from 9.4 to 11.9 mmHg across intervention arms. We conservatively assumed a cross-sectional SD of 14 mmHg and within-person correlation between SBP measures from different end-of-feeding periods of 0.75, which would result in a SD for SBP difference between feeding periods of 9.9 mmHg, a value that is conservative compared to previous trials with similar designs for different patient populations (e.g., 6.1 mmHg from OmniHeart, and between 7.4 and 9.2 mmHg across arms of DASH-Sodium).

4 STATISTICAL ANALYSIS FRAMEWORK

4.1 Overview

This trial is a randomized, four-period crossover study that tests the effects of 4 diets (specified by the combinations of 2 diet factors – DASH4D vs Comparison and 2 sodium levels – Higher vs Lower) on a specified set of outcomes. The 4 diets are denoted DH (DASH4D-Higher sodium), CH (Comparison-Higher sodium), DL (DASH4D-Lower sodium), and CL (Comparison-Lower sodium). Each participant receives all 4 diets. Each diet is eaten for 5 consecutive weeks. The order in which participants eat these diets is random. A break of at least 1 week (typically 2 weeks), where participants are eating their own food, will separate each consecutive set of feeding periods.

		DIETARY PATTERN	
		Comparison	DASH4D
SODIUM LEVEL	Higher (3700mg)	CH (ref*)	DH
	Lower (1500 mg)	CL	DL

\*reference group for the primary contrast

The primary outcome of the trial is end-of-period systolic BP (SBP), with the primary contrast testing the mean SBP difference between the DL and the CH diets (Primary Aim). The secondary contrasts focus on the effects of sodium on SBP stratified by diet types (DH vs DL and CH vs CL, Secondary Aim 1.2.1), and the effect of diet on SBP stratified by sodium levels (DH vs CH and DL vs CL, Secondary Aim 1.2.2). The trial will examine whether the diet and sodium effects are additive through exploring for diet-sodium interaction on SBP (Secondary Aim 1.2.3), and assess the time course of the sodium effects on SBP by diet types (Secondary Aim 1.2.4) and the diet effects on the time course of SBP by sodium levels (Secondary Aim 1.2.5) over the 5-week feeding period. We will also assess the effects of these diet contrasts on other protocol-specified outcomes, namely, diastolic BP (DBP; Secondary Aim 1.2.6), fasting glucose, fructosamine, plasma lipids, CVD risk scores, patient-reported outcomes, and specified safety outcomes, SAEs and adverse medical events (Secondary Aim 1.2.7). We will assess the differences of the aforementioned outcomes under the specified diet contrasts by pre-specified subgroups (Secondary Aim 1.2.8).

Aim	Outcome	Timing	Contrast
Primary 1.1	SBP	End of Period	CH vs DL
Secondary 1.2.1	SBP	End of Period	DH vs DL; CH vs CL
Secondary 1.2.2	SBP	End of Period	DH vs CH; DL vs CL
Secondary 1.2.3	SBP	End of Period	(DH-DL) vs (CH-CL)*
Secondary 1.2.4	SBP	Period Trajectory	DH vs DL; CH vs CL
Secondary 1.2.5	SBP	Period Trajectory	DH vs CH; DL vs CL
Secondary 1.2.6	DBP	Same as all of above for SBP	
Secondary 1.2.7	fasting glucose; glycated albumin; fructosamine; HbA1c; plasma lipids; 24-hour urinary albumin excretion; CVD risk score; patient-reported outcomes	End of Period	CH vs DL; DH vs DL; CH vs CL; DH vs CH; DL vs CL; (DH-DL) vs (CH-CL)*
	safety data (incl. hypoglycemia, hyperkalemia, elevated BP, low BP, SAEs & adverse medical events)	Cumulative over the entire period	CH vs DL; DH vs DL; CH vs CL; DH vs CH; DL vs CL; (DH-DL) vs (CH-CL)*
Secondary 1.2.8	All of above, by pre-specified subgroups		

\*examination of interaction (difference of differences)

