## 10. Study Outcomes and Objectives

Based on prior studies, we hypothesized that salt would have no effect on glucose. Therefore, we plan to combine data from the lower and higher sodium feeding periods for each diet to increase statistical power (i.e., combine data collected during the DASH4D lower sodium diet with data collected during the DASH4D higher sodium diet). Our primary aim is to examine the effects of the DASH4D diet (vs. comparison diet) on glucose control and glycemic variability in adults with type 2 diabetes.

Primary, secondary, and exploratory CGM outcomes were selected based on clinical guidelines and recommendations from a consensus statement on CGM endpoints for clinical trials. CGM outcomes will be based on CGM data captured by sensors worn from week 3 to week 5 (up to 14 days) of each 5-week feeding period in participants included in the DASH4D-CGM ancillary study. Per current analytic recommendations, CGM outcomes will be generated using all available CGM data for each feeding period.

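### For the laboratory glycemia outcomes, the main SAP omits the sodium-averaged diet contrast that Appendix B specifies for CGM glucose in the same trial

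*Combined protocol and SAP*

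**What the plan says.** The trial is a four-period crossover of a 2×2 set of diets, and SAP 4.1 notes "Each participant receives all 4 diets". For SBP, SAP 4.1 states: "The secondary contrasts focus on the effects of sodium on SBP stratified by diet types". Diet effects are likewise taken at each sodium level (SAP 4.3).

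For fasting glucose, glycated albumin, fructosamine and HbA1c (Aim 1.2.7), the contrast table in SAP 4.1 lists "CH vs DL; DH vs DL; CH vs CL; DH vs CH; DL vs CL", followed by the difference of differences. SAP 4.6 describes the same combined and within-level comparisons in words. SAP 4.2.1 extends the Model 1 approach to the continuous outcomes of Aim 1.2.7.

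Appendix B, section 10, starts from the hypothesis that salt does not act on glucose and concludes: "we plan to combine data from the lower and higher sodium feeding periods for each diet to increase statistical power". Sections 10.4 and 11.2 and Table CGM-1 make DASH4D versus comparison, over both sodium levels, the contrast for the CGM outcomes. Sodium effects stay stratified by diet (sensitivity analysis 1a), and the diet-by-sodium interaction is examined (1b). The protocol's change history for v2.6 (November 2024) explains that the previous CGM plan had followed the main SAP by mistake and was returned to the grant's approach. The main SAP is version 1.1, July 2024, and so predates that change.

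**The concern.** The documents hold one hypothesis about sodium and glucose, but only one of the two analysis plans acts on it. CGM glucose gets a diet contrast that uses all four periods of each participant. Laboratory glycemia, measured at the end of those same periods, gets diet contrasts at one sodium level at a time, plus the combined DL versus CH contrast.

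Two things are at stake. First, precision: each within-level diet contrast rests essentially on two of the four periods. Second, comparability: a reader who sets the CGM results beside fructosamine or HbA1c would find no laboratory estimate of the same diet effect. SAP 4.1.4 says that findings from comparisons that were not pre-specified will be marked as such, so an average computed later would carry that label.

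**Working it through.** **Inputs.** From SAP 3: "The trial aims to enroll 100 eligible participants"; "We conservatively assumed a cross-sectional SD of 14 mmHg and within-person correlation between SBP measures from different end-of-feeding periods of 0.75"; detectable differences are given "with 2-sided type 1 error of 0.05 and 90% power". From SAP 4.2.1: Model 1 has period and diet effects with CH as reference, β2 for CL, β3 for DH and β4 for DL. From Protocol 7.3: diet order is balanced and sequences are equally allocated. The documents give no SD or correlation for any glycemia outcome. The SBP figures below therefore only illustrate a ratio.

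1. **The plan's own figure.** SD of a between-period difference = 14 × √(2 × (1 − 0.75)) = 9.90 mmHg. The SAP agrees: "which would result in a SD for SBP difference between feeding periods of 9.9 mmHg". With 1.9600 + 1.2816 = 3.2415, the 90%-power detectable difference is 3.2415 × 9.90/√100 = 3.21 mmHg (3.24 by paired t). The SAP table shows 3.34. This small gap does not affect the ratio in step 3.

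2. **The missing contrast.** At higher sodium, DH − CH = β3. At lower sodium, DL − CL = β4 − β2. Their equal-weight average is (β3 + β4 − β2)/2.

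3. **Standard errors.** With equal variances, a common correlation and balanced sequences, a contrast with coefficients c over the four diets has variance Σc² × σ²(1 − r)/N. For SBP this is Σc² × 196 × 0.25/100 = Σc² × 0.49.
   - Within-level diet contrast: Σc² = 2, variance 0.98, SE 0.99 mmHg.
   - Averaged diet contrast: Σc² = 4 × (1/2)² = 1, variance 0.49, SE 0.70 mmHg.
   - Interaction β4 − β3 − β2: Σc² = 4, variance 1.96, SE 1.40 mmHg.

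   The ratio of averaged to within-level SE is 1/√2 = 0.707, or 29.3% smaller. N, σ and r cancel, so the ratio applies to any outcome that meets these assumptions.

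4. **What that means on the SBP scale.** The detectable difference falls from 3.21 to 3.2415 × 0.70 = 2.27 mmHg, or from the SAP's 3.34 to 3.34/√2 = 2.36 mmHg.

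5. **Sensitivity to the covariance and design.** Generalised least squares standard errors for Model 1 gave ratios of 0.706 to 0.708. The settings were AR(1) and unequal-variance period covariances, four Williams sequences and all 24 orders, and a case with 15 of 96 participants dropping out.

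6. **Where the gain shrinks.** Suppose a share h of the variance of a within-level difference is a person's own response to diet, common to both sodium levels. Averaging does not reduce that part, and the ratio becomes √((1 + h)/2). For h = 0.10, 0.25 and 0.50 (an assumed range) it is 0.742, 0.791 and 0.866, so the SE is 26%, 21% and 13% smaller.

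**The case against.** The strongest reply is that the within-level contrasts are the intended estimands. Protocol objectives 2 and 3 and Aims 1.2.1 and 1.2.2 ask for each factor's effect separately at each level of the other. These effects need no additivity assumption, and additivity is itself a question (Aim 1.2.3). That stands, and it is decisive for SBP and DBP: averaged effects there would be optional summaries that answer a different question.

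A reader might go on to infer that the trial throws away half its information on each factor. The documents do not support this. Model 1 is fitted to all four periods, and the average can be recovered from reported results: with SEs 0.99, 0.99 and 1.40, [2(0.98) + 2(0.98) − 1.96]/4 = 0.49, giving 0.70. What is missing is a pre-specified estimate.

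Three further extensions also fail:
- **A pooled sodium effect.** Appendix B gives no precedent, since it pools diet only and keeps sodium stratified.
- **Safety counts compared on 200 versus 200 participant-periods.** SAP 4.6 uses GEE with log or logit links, so the same combination averages two log ratios. It breaks down if a diet has no events.
- **Making the averaged contrast the leading one for glycemia.** The SAP ranks no contrast for these outcomes, and adding a ranking now would be a debatable late change.

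It can also be said that CGM metrics and laboratory assays are different outcomes, and that the v2.6 history explains why the plans diverge. Both are true. Neither explains why the hypothesis about sodium and glucose should inform one set of outcomes and not the other.

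**Conclusion.** The point holds for fasting glucose, glycated albumin, fructosamine and HbA1c only. It is a minor, worthwhile addition and not the correction of an error. The gain is an SE up to 29% smaller than that of a within-level diet contrast, under Model 1 with balanced sequences and a common within-person correlation. It is about 13% to 26% smaller over the assumed range of person-specific response. No absolute gain in glycemia units can be stated, because the documents give no variances for these outcomes.

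The average does not require sodium to have no effect on glucose, since each sodium level counts equally for both diets. It does lose meaning as a single effect if sodium modifies the diet effect. The primary contrast, its power and the stratified contrasts are untouched.

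**What to change.** In SAP 4.1 (table row for Aim 1.2.7) and SAP 4.6, add one pre-specified contrast for the four glycemia outcomes: the diet effect averaged over sodium, (β3 + β4 − β2)/2 from Model 1, with its 95% CI.

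- Report it beside all existing contrasts and the interaction estimate with its CI.
- Label it as an average over the two sodium levels.
- Do not make it conditional on the interaction test. The interaction has twice the SE of the average (1.40 against 0.70 on the SBP scale), and SAP 4.4 says the trial is not powered for it.
- State the amendment's date relative to unblinding. Protocol 7.3 leaves the trial statisticians unmasked to outcome data, and Protocol 15.2 describes the specimens as already collected.

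The cost is one linear combination per outcome from a model already planned. The downside is one more unadjusted secondary estimate per glycemia outcome, and one that is only an average if sodium modifies the diet effect.
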